2.3.2 Protection against Risks

Study procedures will be reviewed and approved annually by the University of Wisconsin Health Sciences Institutional Review Board. Participants will be completing this intervention in their own home, and will be directed to stop exercising immediately if they experience any chest pains or abnormal symptoms such as dizziness, faintness, nausea etc. Additionally, in order to maximize participant safety and well-being, several strategies will be implemented to protect against and minimize any potential risks and to protect the privacy of all participants. Including:

- All participants will be screened with a telephone interview to determine their health status, eligibility, and ability to participate in aerobic exercise (Physical Activity Readiness Questionnaire; PAR-Q)
- Although the exercises will be completed at home, participants will be instructed to discontinue exercise if they experience any dizziness or light-headedness or pain in their chest. We will recommend that participants with continued issue to seek out their primary care physician.
- To minimize risks to confidentiality, participants will be assigned a study ID number to be used in place of their name. The only document linking study ID number and the participant's name will be kept separate from the data used for data processing and analysis. Only authorized study personnel will have access to the data. Electronic data will be coded and entered into a secured file on the Physical Activity Epidemiology lab server which is located in a password protected area with firewall protection and backed up daily. Moreover, the screening data for eligible participants will be kept and secured in a locked file cabinet in the Physical Activity Epidemiology lab until the participant has either completed the study, removed themselves from participation, or is excluded from participation. All screening data for eligible participants will be shredded upon participant completion, dropout, or exclusion from the study. Phone screening data from any interested potential participants not meeting inclusion criteria will be shredded immediately.
- If used, web-based surveys and their accompanying database will reside on a secure survey server. No private health information will reside on the survey server, only randomly generated ID numbers. Survey information will then be pulled into the secure database.

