6.3 Exclusion Criteria

Exclusion Criteria	
1.	Absolute contraindications to exercise (i.e., acute myocardial infarction, severe orthopedic or musculoskeletal limitations)
2.	Have evidence of recurrent or metastatic disease
3.	Are currently performing resistance training ≥ 2 days per week
4.	Report of chest pain, shortness of breath, fainting, or angina pectoris
5.	Have physical disability that would limit range of motion through exercises such as sitting, standing and inability to walk one block
6.	Plans to move from the area
7.	Enrolled in another clinical trial or has used of any investigational drugs, biologics, or devices within 30 days prior to randomization
8.	Women who are pregnant or breast-feeding
9.	Not suitable for study participation due to other reasons at the discretion of the investigator

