or demonstrate issues with exercises or their form. At the mid-point of the study, participants will receive an email with the questionnaires, so that the questionnaires will be done at baseline, at the study mid-point, and at the final visit.

Participants in the intervention group will also complete accelerometer (Actigraph) assessments at three study points: Early in the intervention near the instructional visit, at the mid-way (5-week) mark, and before the final visit. These accelerometers will be sent and received via mail and participants will receive instructions on how to wear, use and send to us during the instructional visit.

At the end of the 10 week period, participants will return to the UW campus for a final visit to repeat baseline study measures. At this time, intervention arm participants will also complete an exit-style interview with the study coordinator to help improve the intervention for future participants. This will be recorded, but anonymized upon transcription.

While the formal intervention period will be 10 weeks in duration, we will continue to follow those in the exercise arm for five weeks post-final assessment. This follow up period will consist of surveys to the participants assessing the frequency of the home-based resistance exercise, to determine if the behavior of exercise persists in the short-term following intervention conclusion.

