 - **When collected:** Baseline, mid-point (~5 weeks), final visit (~10 weeks)
- **Self-efficacy.** This will be assessed using the validated self-efficacy for exercise scale, modified for specificity to strength training.³⁴ These measures will be repeated at the study mid-point (5 weeks) to assess changes over time.
 - **When collected:** Baseline, mid-point (~5 weeks), final visit (~10 weeks)
- **Adherence.** Compliance and adherence will be measured via detailed exercise logs. A participant needs to complete at least 50% of the prescribed exercises in a session to be considered adherent to the session.
 - **When collected:** ongoing, logs will be completed throughout the intervention and submitted at the final visit
 - Additionally, for those in the intervention arm, we will ask that they continue to conduct the prescribed exercises for an additional five weeks after study completion. Participants will still submit paper logs, and this adherence measure will allow for study of adherence without prescribed check-ins from the study coordinator over the five week period.
- **Acceptability.** Participants will participate in a semi-structured qualitative interviews with the study coordinator. Interviews will be recorded, transcribed and coded to identify content themes. These interviews will be used to collect qualitative information and overall satisfaction with the intervention, as well as areas to improve with future interventions and barriers to participation.
 - **When collected:** Final visit (~10 weeks)

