8.2 Video calls

Participants will receive a tablet for the duration of the intervention for video conferencing with research team. Phone call conferencing will be available, however the tablets allow for video applications so that participants can visually interface with members of the research team. Additionally, using video conferencing allows participants to receive feedback and form recommendations from her home if she has questions or would like feedback on her performance for specific exercises. However, because this is a pilot intervention, we aim to determine if the video

conferencing component is useful. By providing each participant with a tablet, we are inclusive for individuals who may not have access to these resources on her own. Each participant will receive a check-in at eight points during the 10 week study: two calls in the first week, one during weeks three four and five, one during week six , and finally one during week eight consistent with their preferred contact method to provide feedback on their progress and resistance training. The study coordinator will ask about overall qualitative satisfaction, and issues the participant is having, and any questions that the study coordinator could potentially address. Participants are welcome to reach out to the lab or study coordinator at any point during the study, however these pre-planned check in visits will hopefully facilitate discussion if any issues remain unaddressed.

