8.5 Study Visits

8.4.1 Screening/Baseline:

Baseline. At this visit, the study coordinator will explain the study and obtain written informed consent. Physical measurements (anthropometrics, blood sample, DXA scan, functional fitness testing) will be completed. The study coordinator will instruct the participant on how to properly wear the accelerometer (to be returned via pre-paid mailer), complete a 7-day PA log, and complete the online questionnaires.

Randomization. After all baseline measures have been completed and checked, the participant will be randomized with 1:1 probability to the intervention or wait-list control group. A blocked randomization scheme will ensure equal allocation of participants to each group. Participants will be notified of their group assignment by phone; those in the intervention group

Table 4. Acceptable Window for Study Visits (including weekends)

Visit	Window	Activities
Randomization	+/- 5 days	Allocate to group
Instructional visit	+/- 2 weeks	Teach exercises, learn how to interface with software, how to log exercises
Final visit	+ /- 2 weeks	Collect final measures

8.4.3 Unscheduled:

- Pain or concerns that need to be addressed in person
- Adverse event follow ups with PCP

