10.4 Data and Safety Monitoring

The Site Investigator ([name]) will be responsible for reviewing and monitoring all study data and any adverse events for this study. The Investigator will meet with study personnel at least weekly to evaluate study progress, including periodic assessment of data quality and timeliness, participant recruitment, accrual and retention, participant risk versus benefit, and other factors that can affect study outcomes. All unanticipated problems regardless of where they occur, will be reported to the University of Wisconsin IRB.

This protocol is considered to have a minimal risk to participants, as it prescribes physical activity that is consistent with national recommendations and guidelines for cancer survivors. We attempt to reduce the risk of injury or muscular soreness by excluding individuals who report difficulty transitioning from sitting to standing, walking 1 block (as a proxy measure of basic physical functioning), or report that they are otherwise unable to work towards the intervention goals. As with any exercise intervention, there is also a minor risk of cardiovascular events. Participants in both intervention groups will receive regular check-in calls to assess progress and address any potential problems regarding physical issues or emotional stress.

11 Assessment of Safety

This protocol is considered to have a minimal risk to participants, as it prescribes physical activity that is consistent with national recommendations and guidelines for cancer survivors. We attempt to reduce the risk of injury or muscular soreness by excluding individuals who report difficulty transitioning from sitting to standing, walking 1 block (as a proxy measure of basic physical functioning), or report that they are otherwise unable to work towards the intervention goals. As with any exercise intervention, there is also a minor risk of cardiovascular events. Participants in both intervention groups will receive regular check-in calls to assess progress and address any potential problems regarding physical issues or emotional stress.

12 Study Finances

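### For chest pain or fainting in home training that resolves, no visible text requires a prompt report or a pause for medical review (2.3.2)

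*Combined protocol and SAP*

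**What the plan says.** Section 2.3.2 states the stop rule twice: women exercising at home must stop for chest pain, dizziness, faintness, light-headedness, nausea or similar symptoms. The only step after stopping is a recommendation tied to persistence: "We will recommend that participants with continued issue to seek out their primary care physician". No condition for resuming is given.

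At entry, 6.3 (criterion 4) excludes on "Report of chest pain, shortness of breath, fainting, or angina pectoris". Sections 10.4 and 11 accept that "there is also a minor risk of cardiovascular events".

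Several other provisions bear on the point:

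- Coaching calls, the last one listed in week 8 (8.2, Appendix 1), and an open invitation: "Participants are welcome to reach out to the lab or study coordinator at any point during the study".
- Unscheduled visits (8.4.3), including "Adverse event follow ups with PCP".
- Safety assessments at 4-6, 10 and 15 weeks (Table 3).
- PAR-Q screening (2.3.2), teaching on normal training symptoms at the instructional visit, and withdrawal for a safety reason (7.7.1).
- Weekly staff meetings, and a Site Investigator who "will be responsible for reviewing and monitoring all study data and any adverse events for this study" (10.4).

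In weeks 11-15 the exercise arm keeps training, by design without coordinator check-ins (8.1). Section 8 describes the contact in that period as "surveys to the participants assessing the frequency of the home-based resistance exercise".

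**The concern.** Chest pain or fainting on exertion can matter medically even when it passes within minutes. At screening the plan treats a report of either as a reason to exclude. After randomization, the written response to an episode that resolves ends with stopping. Nothing visible makes the woman tell anyone soon, and nothing visible has a physician decide whether she should go on.

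Two things are at stake. The first is the safety of women in the exercise arm over all 15 weeks of training. The second is the primary safety endpoint, the number of adverse events during the intervention (4.1.3): a brief episode that is recalled weeks later, or never mentioned, can drop out of that count.

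**Working it through.** The plan gives no figure to reproduce. The check is a comparison of texts plus a count of scheduled contacts.

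**Does any visible text require a prompt report, or a pause until review, after a resolved episode?**

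- 2.3.2: requires stopping; recommends a physician only if the problem continues.
- 8.2: contacting staff is optional.
- 8.4.3: foresees physician follow-up of adverse events, but sets no symptom trigger, deadline or hold on training.
- 10.4: review of adverse events and weekly meetings work on what staff already know. Section 11 repeats the risk text and adds no pathway.
- 7.7.1: allows withdrawal for safety, with no symptom criterion and no temporary hold.
- Section 2, Key Roles: names a co-investigator as medical monitor, but no visible text gives that role symptom review.

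None of these requires either step.

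**Do the entry rule and the stop rule cover the same symptoms?** Only chest pain is named in both. Criterion 4 lists fainting; 2.3.2 lists faintness, which is not the same. Dizziness, light-headedness and nausea are not in criterion 4. Shortness of breath is in criterion 4 but is not named in 2.3.2.

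**Sessions after the last listed call.** Inputs: two sessions a week for 10 weeks, continued for 5 (Section 8).

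- Intervention: 2 × 10 = 20 sessions. Follow-up: 2 × 5 = 10.
- Weeks 9-10: 2 × 2 = 4 sessions, and 4/20 = 20% of the intervention. This counts the week-8 sessions as before the call; if both came after it, the figure would be 6/20 = 30%.
- Weeks 11-15: 10 further sessions. The intervention is 10 weeks (4.1), so these fall outside the adverse event endpoint and count for participant safety only.

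Section 8.2 states eight calls, but its listed weeks (1 twice, 3, 4, 5, 6, 8) give seven, as does Appendix 1 (1A, 1B, 2, 3, 4, 6, 8). Both end in week 8. If an unplaced eighth call fell in week 9 or 10, the exposure would be smaller.

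**Time to the next scheduled contact.**

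- Up to week 8, the longest gap between calls is about 2 weeks on either list.
- Week-8 call to week-10 visit: 10 − 8 = 2 weeks, or 2 + 2 = 4 with the visit window (Table 4).
- Week-10 to week-15 Safety assessment: 15 − 10 = 5 weeks.
- The exercise log has a line for concerns (Appendix 3). Section 8.1 says "logs will be completed throughout the intervention and submitted at the final visit", while Table 3 lists logs as weekly. A week-1 entry would reach staff after about 1 week (weekly return), 10 − 1 = 9 weeks (final visit), or 9 + 2 = 11 with the window.

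**Cost of a pause, keeping paused sessions in the denominator.** Assume primary adherence is taken over the 20 intervention sessions, with 40/2 = 20 women in the arm.

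- One week: 2/20 = 10% of her sessions, so her best possible adherence is 18/20 = 90%. The arm mean falls by at most 10/20 = 0.5 percentage points.
- Two weeks: 4/20 = 20% of her sessions. The arm mean falls by at most 20/20 = 1.0 point.

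**The case against.** The strongest reply is that 2.3.2 describes what participants will be told and is not itself the instruction. The consent form is a separate document (7.6.2), the instructional materials are not reproduced, and some pages are not available. Any of these may already tell women to report and wait. This stands as a limit on the finding, and it shapes the fix.

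It can also be said that this is a minimal-risk band-and-dumbbell pilot with screening, regular calls, weekly staff meetings and safety assessments. That is true and it lessens the gap. It does not close it, because each of these depends on the episode being volunteered, asked about or already known.

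A reader might go further than the documents allow in four ways:

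- That the women train alone. The text says they train at home; it does not say that nobody else is there.
- That the plan permits training to resume. It is silent, and the instruction to discontinue could mean more than ending one session.
- That every symptom in the stop rule would have excluded the woman at entry. Only chest pain is named in both places.
- That (4 + 10)/30 = 47% of sessions are a hole in the adverse event endpoint. That share mixes in follow-up weeks outside the 10-week intervention; 4 of 20 is the relevant figure.

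**Conclusion.** The point holds on the visible text. Section 2.3.2 sets an actual rule, and for chest pain or fainting on exertion that resolves, that rule stops short of a prompt report and a pause for medical review. This is more than a missing detail, because following the rule as written gives weaker protection than the plan's own entry criterion implies. It should be changed, though nothing here invalidates the design or the analysis.

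The size is 4 of 20 intervention sessions (20%) after the last listed call, with the next scheduled contact about 2 to 4 weeks away, plus 10 follow-up sessions without check-ins. A reader might infer that events will be missed. The documents give no event rate, so these are exposures and possible delays only. The conclusion assumes that week 8 is the last call and that the unseen consent form and materials do not already contain the instruction. Confidence is medium for that second reason.

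**What to change.** In 2.3.2, and on the summary sheet handed out at the instructional visit, give one instruction for chest pain, fainting or near-fainting, or unusual shortness of breath during exercise. The woman calls emergency services if it is acute, tells study staff promptly, and pauses training until the medical monitor or another study physician has reviewed the episode and documented a decision, even if it has resolved. Apply this through week 15. In 10.4, assign the review and require that the episode be recorded as an adverse event.

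Other symptoms, such as brief dizziness or nausea, can stay under the current stop rule with a report to staff. If the consent form already has the instruction, carry it into 2.3.2.

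State how paused sessions count: keep them in the prescribed total for the primary adherence analysis, and also report adherence without them.

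The change is cheap: amendment wording, a line on an existing sheet and a little time from staff already in place. The downside is some paused sessions, possibly a few women leaving, and slightly lower adherence against the 90% target.

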2.3.3 Potential Benefits to the Subjects

There are no anticipated benefits to the participants in this research study.

2.3.4 Risk Minimization:

No drug, biologic, or dietary supplement will be used in this study. To minimize risk, participants will undergo distal finger pricks to collect blood samples as opposed to traditional venipuncture for collection of blood biomarkers. No other laboratory tests will be conducted.

3 Study Aims

- **Aim 1:** To determine the feasibility of recruiting and retaining endometrial cancer survivors to a home-based resistance training 2 sessions per week of 20-40 minutes of exercise.
- **Aim 2:** To determine participant satisfaction with each component of the intervention and identify opportunities for refinement of the intervention prior to testing in a larger study.
- **Aim 3:** To establish that functional and objective assessments are feasible and well-tolerated in enrolled participants, as assessed using the functional fitness test (FFT) battery, dual-energy x-ray absorptiometry (DXA), finger-pricks for dried blood spots and patient-reported outcomes.

4 Study Design and Endpoints

4.1 General Design

- A phase III, randomized, two-arm trial with a wait-list control group
- The intervention itself is 10 weeks, with an additional five week follow up assessment for those in the exercise arm to determine adoption of the program. Overall, the anticipated total duration should be 20 weeks for participants
- The intervention will consist of (a) an initial in-person instructional session; (b) instructional materials and resistance training equipment (e.g., resistance bands) and (c) support and feedback provided via video coaching sessions; and (d) a final in-person study visit to collect post-study measures for both groups

4.1.1 Primary Study Endpoints

The primary endpoint is adherence to prescribed exercise sessions as measured using exercise logging and video sessions of exercises.

4.1.2 Secondary Study Endpoints

Secondary endpoints to be measured include qualitative satisfaction with intervention, blood biomarkers, lean muscle mass, body composition, functional fitness performance, self-efficacy, quality of life measures, and accelerometer-measured physical activity.

4.1.3 Primary Safety Endpoints

The primary safety endpoint will be total number of adverse events over the duration of the intervention.

5 Study Infrastructure

The general infrastructure for this study will include an overall PI ([name]). There will be additionally one primary biostatistician for the study, and one main study coordinator who will be responsible for managing daily study operations.

6 Study Subjects – Enrollment and Withdrawal

- Accrual Goal: The study aims to enroll 40 participants over a one-year period. Subjects will be identified through their clinician/oncologist to determine interest in the study before being screened over the telephone by study staff.
- Participants will be screened over the phone to determine eligibility, and enrollment in the study will occur after screening by both the clinician/oncologist and research staff. The screening procedures will be performed under a separate screening consent form.

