2.3 Potential Risk and Benefits to Subjects

2.3.1 Known Potential Risks

Potential risks of participating in this study include musculoskeletal soreness and a possible loss of confidentiality, either through the breach of non-identifiable data collected online, or through the breach of secure study databases or physical files.

Potential Benefits of the Proposed Research to Human Subjects and Others: Findings from the proposed study will contribute to the scientific knowledge of the feasibility of resistance training interventions in endometrial cancer survivors. Additionally, the knowledge gained will contribute to the scientific knowledge aimed at understanding the potential therapeutic benefits of resistance training exercise for endometrial cancer survivors. The risks of our study procedures are low and therefore are seen as justifiable in regards to the knowledge to be gained.

Importance of Knowledge to be gained: Increasing physical activity after a cancer diagnosis is an important area of researching, and finding feasible interventions for endometrial cancer survivors are key to sustainable lifestyle changes. This research will take the first step that will provide valuable information and serve as a scaffolding for the continued design and development of future interventions.

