8.3 Labs

Blood spots: In a non-clinical setting, dried blood spots collected using finger pricks are a low-cost way to establish the feasibility of biomarker data collection. Using a standardized protocol, participants will undergo a fingerpick to collect a peripheral blood sample to assess glycosylated hemoglobin (A1c) and c-Reactive Protein⁵⁰ via dried blood spots. Dried blood spots can be collected by non-phlebotomists in non-clinical settings, and the values for both A1c and CRP are highly correlated between dried blood spots and venipuncture.⁵¹

8.4 Established Standard of Care:

There are currently no established standards of care in terms of prescribing exercise (especially resistance training exercise) in endometrial cancer survivors.

Table 3. Study Calendar of scheduled measures

Modifications proposed				
	Baseline	4-6 Weeks	10 Weeks	15 Weeks
Demographics	✓			
Cancer characteristics	✓			
Anthropometrics	✓		✓	
Body composition	✓		✓	
Biomarkers (blood spots)	✓		✓	
Physical activity (self-report)	✓	✓	✓	
Physical activity (device ¹)	✓	✓	✓	✓
Functional fitness	✓		✓	
Quality of life	✓	✓	✓	
Self-efficacy	✓	✓	✓	
Satisfaction & feedback	✓	✓	✓	✓
Safety		✓	✓	✓
Additional data collected during intervention:				

 • Adherence logs (weekly) • Coaching call completion 				
<small>¹We will be using accelerometers for data collection, as opposed to Fitbits in the original proposal, as accelerometers are the gold standard physical activity measure</small>				

will be scheduled for the intervention introductory session. (Those in the wait-list control group will receive this session at the same time as the final measures are collected.)

Instructional. Participants randomized to the intervention group will meet with study coordinator to learn how to conduct the exercises, how to use the materials, how to complete the exercise log and general instructions on the normal symptoms of resistance training. This visit should take 1-2 hours, ensuring the participant is confident.

8.4.2 Follow up:

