9.1 Sample Size Determination

Sample Size and Power. The purpose of this trial is not to conduct hypothesis testing, but rather to field-test the intervention to identify adherence rates to exercise prescription across a group of participants. At this time, the anticipated effect size is unknown and the sample size of 40 has been selected to maximize feasibility in the anticipated time frame for this project.

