9.3 Subject Population(s) for Analysis

The populations for this investigation include:

- All-randomized population: Any subject randomized into the study, regardless of whether they received study agent
- All-treated population: Any subject randomized into the study that received at least the instructional visit of the intervention
- Protocol-compliant population: Any subject who was randomized, was allocated to the exercise group and provided at least one set of data elements required by the protocol.

9.3.1 Describe the types of analysis:

- **Primary Analysis:** The primary objective includes measuring the percentage of completed sessions compared to prescribed, and a one-sample t-test will be conducted to determine if that proportion, across participants, is >90%. A one-sample t-test will be done to determine if retention is >90%.

- **Secondary Analyses:** The secondary analyses includes measuring the objective and functional changes from pre to post intervention as well as differences between groups. Paired ANOVAs and descriptive statistics will be used to analyze functional and objective data, as well as participant feedback data, including satisfaction with each component of the intervention.
- **Exploratory, longitudinal analyses:** Content analysis will be done on the qualitative interviews to examine barriers to physical activity, as well as satisfaction with the intervention, and identification of themes to improve the intervention. Although formal hypothesis testing is not part of our specific aims, we will conduct longitudinal analyses of the data we collect to estimate potential magnitude of expected changes, as well as longitudinal analysis of the repeated measures.
- **Safety Analysis:** The safety analysis includes simple descriptive analysis about the number of adverse events over the course of the intervention between groups and across sites.

9.4 Planned Interim Analysis:

There are no planned interim analyses for this investigation.

10 Data Collection, Handling and Record Keeping

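### The primary safety result is a raw total of adverse events, which repeated soreness reports from a few exercise-arm women could inflate; women affected per arm should lead

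*Combined protocol and SAP*

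**What the plan says.** Section 4.1.3 sets the endpoint at the level of events: "The primary safety endpoint will be total number of adverse events over the duration of the intervention". The safety analysis in section 9.3.1 keeps that unit and plans a "simple descriptive analysis about the number of adverse events over the course of the intervention between groups".

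Section 2.3.1 names the most likely event: "Potential risks of participating in this study include musculoskeletal soreness". At the instructional visit, exercise-arm women receive "general instructions on the normal symptoms of resistance training". The plan does not say whether those symptoms are recorded as adverse events or, if they are, whether a recurrence is a new event.

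Sections 10.4 and 11 give no adverse event definition, no seriousness or relatedness classification and no count of women affected. Table 3 has a safety row at 4-6, 10 and 15 weeks but does not say what is asked or how it is counted.

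On arm size, section 9.1 says "the sample size of 40 has been selected to maximize feasibility in the anticipated time frame for this project", and section 8.5 says "the participant will be randomized with 1:1 probability to the intervention or wait-list control group".

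**The concern.** An event total gives the same weight to one woman who reports soreness ten times and to ten women who each have a different problem. In this design the opportunities to report are lopsided. Exercise-arm women have a programme of sessions, a log for each session with comment and concern fields, and scheduled coaching calls. Wait-list women do not start the programme until their 10-week visit. With about 20 women per arm, two or three frequent reporters can determine the total.

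The pilot is meant to inform a larger trial (section 2.1). A safety summary that shows an excess in the exercise arm, when the excess is a few women's repeated soreness, would be carried forward as if it described how many women were harmed.

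**Working it through.** The plan states no adverse event rate, threshold or power for safety, so it has no safety figure to reproduce. The check asks how far a total and a count of women can diverge at this sample size.

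**Inputs from the plan**
- Women per arm: 40 / 2 = 20 (sections 8.5 and 9.1).
- Prescribed sessions per exercise-arm woman: 2 per week × 10 weeks = 20 (section 8).
- Coaching calls: eight stated in sections 8 and 8.2, but the schedule in 8.2 itemises 2 + 3 + 1 + 1 = 7.
- Table 3 safety assessments within the 10 weeks: two (4-6 and 10 weeks).

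**Assumed inputs:** all event counts, background rates and numbers of repeats.

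**Arithmetic.** Let W exercise-arm women be affected. Of these, k report only soreness, m times each, and the others have one event each. Then total events E = (W − k) + k·m, and the repeaters' share is k·m / E.

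Take W = 6 and k = 3, with 8 wait-list women having one event each. Women affected are 6/20 = 30% against 8/20 = 40% for every m.

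| m | Why this value | E = 3 + 3m | Wait-list total | Repeaters' share |
|---|---|---|---|---|
| 2 | one per Table 3 assessment | 9 | 8 | 67% |
| 5 | intermediate | 18 | 8 | 83% |
| 7 | one per itemised call | 24 | 8 | 88% |
| 20 | one per session | 63 | 8 | 95% |

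The total ranks the arms opposite to the count of women in every row, though by a single event when m = 2.

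Two variants show the limits:
- With 8 women affected in each arm, k = 3 and m = 5, E = 5 + 15 = 20 against 8. This is inflation only.
- With W = 4, k = 1 and 8 wait-list women, E = 3 + m. That is 5 against 8 at m = 2 (no reversal), 8 against 8 at m = 5, and 10 against 8 at m = 7.

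**Simulation.** 50,000 trials of 20 against 20, with Poisson background events at assumed means of 0.25, 0.5 and 1.0 per woman. Three exercise-arm women have five added soreness reports each.

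| Result | 0.25 | 0.5 | 1.0 |
|---|---|---|---|
| Mean totals, equal background rates | 20 v 5 | 25 v 10 | 35 v 20 |
| Exercise total at least double, with repeaters | 98% | 79% | 33% |
| Same, without repeaters | 18% | 8% | 2% |
| Ranking reversed, equal background rates, with repeaters | 13% | 22% | 28% |
| Ranking reversed, exercise background at half the wait-list rate, with repeaters | 31% | 58% | 60% |
| Same, without repeaters | under 1% | under 1% | under 1% |

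Reversed means a higher exercise total with fewer exercise women affected.

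**What the proposed summary would show** in the first illustration, using exact (Clopper-Pearson) 95% intervals. For x of n, the limits are the 2.5% quantile of Beta(x, n − x + 1) and the 97.5% quantile of Beta(x + 1, n − x).
- Women with an event other than soreness: 3/20 = 15% (3.2% to 37.9%) against 8/20 = 40% (19.1% to 63.9%).
- Exercise-arm women with soreness: 3/20 = 15%.

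These lines do not change with m.

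**The case against.** The strongest reply is that nothing shows soreness will be counted. Teaching women the normal symptoms of training, and listing pain or concerns separately from adverse event follow-ups among the unscheduled visits in section 8, both hint that routine soreness may not be an adverse event. This stands. A reader might infer that the safety result will be driven mainly by soreness, and the documents do not support that. They only fail to rule it out.

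A second reply is that reversal is a special case. This also stands: it requires more affected women in the wait-list arm, and the half-rate scenario has no basis in the plan. Otherwise the effect is inflation, which weakens as background events become common.

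Third, the practical harm is limited. The comparison is descriptive, with no test, threshold or interim analysis. Section 10.4 has the investigator review adverse events and meet staff at least weekly, so a serious event would be seen individually. This limits the harm to the reported summary but does not make the total a good one.

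Fourth, counting women is not a cure by itself. If soreness counts, women with at least one event could also be mostly women with soreness. Nor does the change of unit correct unequal collection between arms. Both points are right and shape the fix.

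**Conclusion.** The point holds in conditional form. The primary safety result is a raw event total and nothing visible in the plan reduces it to women affected. If soreness is recorded and repeats are counted, three women are enough to turn 8 wait-list events into a comparison of 18 against 8 (five reports each) or 24 against 8 (seven each), with fewer exercise women affected. If collection is confined to the two assessments in Table 3, the same case gives only 9 against 8. All event counts and rates are assumptions.

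Three stronger readings are not supported:
- A reader might infer that the total undermines the minimal-risk statement in sections 10.4 and 11. That statement rests on consistency with exercise guidelines and on the exclusions, not on the event count.
- A reader might cite the wide bound after no serious events among 20 women: one-sided 95% upper limit 1 − 0.05^(1/20) = 13.9%, or two-sided 1 − 0.025^(1/20) = 16.8%. That reflects the arm size and is the same whether events or women are counted.
- A reader might infer that early leavers leave the total without a usable denominator. Section 9.3 defines analysis populations and section 6.4.3 expects about 5% loss, so adjusting for time in study would change little.

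The change is worth making before data are summarised, but the plan contains no test that this could invalidate.

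**What to change.** In sections 4.1.3 and 9.3.1, make the primary safety summary the number and percent of women per arm with (a) at least one adverse event other than expected muscle soreness and (b) at least one serious or exercise-related event, each with an exact 95% interval. Keep non-serious expected soreness out of (b) as well, or it will return through relatedness. State how expected soreness is identified.

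Report women with soreness, and the total number of events, as separate secondary summaries.

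Reconcile the text on check-in calls. Sections 10.4 and 11 say both groups receive them, whereas section 8 and Appendix 1 schedule them for the intervention group. Section 8.2 refers to each participant and states eight contacts while itemising seven. The aim is that adverse events are collected in the same way in each arm.

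The cost is a seriousness, relatedness and expected-soreness entry for each recorded event, made when it is recorded because these are hard to reconstruct later. These entries involve judgement, which is one reason to keep soreness and the total visible. The sample size does not change.
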